2.2.4 Acceptability of and engagement in the intervention (RQ iv)

This will be determined by in-depth qualitative interviews (guided by Stirling University) transcribed and analysed using a thematic framework approach. A random sample of 1 in 3 participants (n=10) stratified by degree of engagement with the intervention will be invited for interview at the end of phase 2 and again (another 10 participants) at the end of phase 3. These interviews will explore patient views on recruitment methods and timing, assessment procedures, programme content, activity and body weight goals, delivery, duration, intensity and exit strategy. In addition, participants will be asked to discuss factors influencing adherence including personal beliefs, motivation, family members, social and NHS staff support.

Interviews will also be conducted the two lifestyle coaches and the research nurse, who are members of the research team, for their views and feedback of the intervention delivery.

2.2.5 Cost of intervention delivery (RQ v)

This will be assessed from lifestyle counsellors' time sheets plus any additional consumable costs per person.

3 STUDY DESIGN

This study will be a single arm, single centre feasibility study of the TreatWELL intervention programme.

3.1 STUDY DESCRIPTION

The TreatWELL intervention programme aims to facilitate collaboratively agreed stepped behaviour changes towards achieving and maintaining smoking cessation, increasing physical activity to at least 150 minutes moderate intensity activity per week, caloric intake appropriate to weight status and a nutrient dense diet. It will be initiated shortly after diagnosis (pre-surgery) and continued until 25 weeks after the end of the surgical recovery period (i.e. during adjuvant therapy and when patients are adjusting to normal life and re-establishing eating and activity habits). The programme will be delivered by lifestyle counsellors (LCs) by three face to face contacts and a minimum of 12 phone calls supported by written literature and a range of behavioural techniques. The intervention will be delivered on a one to one basis (due to restricted time frame between diagnosis and treatment commencement which inhibits group sessions). Total intervention period; 3 weeks in phase 1, 3 weeks in phase 2, 25 weeks in phase 3; total intervention period 31 weeks.

Delivery Phases

Participants will receive the TreatWELL personalised intervention programme delivered in three phases. The duration of each phase is based on NHS clinical experience. Decisions about phase completion and progression will be made in conjunction with the clinical nurse specialist (CNS).

Phase 1 Pre-habilitation to start within 3-10 days of diagnosis to surgery The current target is for treatment to start within 31 days of diagnosis. Pragmatically it is likely that a minimum of three weeks pre-habilitation can be achieved for all participants.

Phase 2 Surgical recovery to start 1 day post-op and aim to complete within 21 days This phase is estimated at three weeks of post –operative recovery prior to commencing rehabilitation or start of adjuvant therapy. This phase will cover the period when ERAS (Enhanced Recovery After Surgery) procedures are on-going as part of usual care.

Phase 3 Post surgical / adjuvant therapy recovery to start 21 days post-op for 25 weeks This phase will ensure that all participants are supported during adjuvant therapies (which may be variable in delivery period) and then when re-establishing daily habits. The period is designed to allow a minimum of 10 weeks post treatment for all.

Theoretical basis

All goals are consistent with the American Cancer Society and World Cancer Research Fund guidance for cancer survivors. The behavioural approaches are informed by two main theoretical frameworks: self-regulatory theory and the health action process approach. At each phase of the programme, personalised, specific goals will be identified with a focus on two health behaviours that are selected as a priority for that individual (e.g. smoking, physical activity). All participants will be asked to engage a support person (e.g. spouse) to assist in their adherence with the programme.

Programme content

Smoking

In phase 1 all participants who smoke will be offered a referral to smoking cessation services in the community. Under the national pharmacy contract, public health element, all community pharmacies are commissioned to offer smoking cessation support. In most pharmacies this consists of a brief intervention, one to one support and the provision of free nicotine replacement therapy (NRT) and assessment to meet the needs of the participant. These services will be promoted again as necessary in phases 2 and 3.

Physical activity

In phase 1, participants will be seen for a one hour session where at least 40 minutes will focus on improving cardiovascular fitness prior to surgery. Each participant will be set personalised, ability appropriate physical activity goals aiming towards achieving and/or maintaining 20-25 minutes moderate intensity activity per day (150 minutes per week) plus exercises designed for cardiovascular fitness and muscular strength. If current physical activity is already at that level, participants will be encouraged to maintain this and a modest increase will be encouraged. Participants will be encouraged to develop personalised action and coping plans. Activities (e.g. brisk walking) will be demonstrated and tried by participants and daily goals set. Two telephone calls will be made to participants in the pre-surgery period to enhance compliance and identify and discuss challenges. Personal activity goals will be based on activity levels at baseline measures. Written support material and an exercise DVD will be loaned.

In phase 2, participants will be encouraged to commence activity in accordance with ability, post-op condition and guidance from collaborating physiotherapist.

In Phase 3, the initial instruction procedure will be repeated and expanded to include emphasis on core strength, mobility and functional ability, with a strict protocol for referral to physiotherapist on any safely issues concerning risk of infection, hernias etc.

Dietary intake and alcohol

In all 3 phases, participants will undergo nutritional screening using the malnutrition universal screening tool (MUST). Participants at risk of malnutrition will be referred to the NHS dietician (as per usual care) for all dietary management. Participants will continue with other aspects of the programme (e.g. smoking cessation and improved physical activity) delivered by the LCs.

In phase 1, advice for participants not at risk of malnutrition (BMI>20kg/m²) will focus on avoiding weight gain and increasing nutrient quality of diet in line with the department of health eatwell model (www.gov.uk/governmenr/uploads/system/uploads/attachment_data/file/ 153475/dh_129974.pdf). Participants will also be advised about decreasing alcohol intake, as appropriate. No energy prescription will be set in phase 1.

In phase 2 and initially in phase 3, nutrition advice will focus on symptom management (e.g. anorexia, vomiting and bowel problems) and work towards achieving a nutrient dense diet. All participants (BMI>20kg/m²) will be given personalised guidance on a nutrient dense diet and avoidance of excess weight gain. Participants with a BMI>25kg/m² will be advised on avoidance of weight gain and modest weight reduction (>5% weight loss) using a personalised energy prescription goal.

Behavioural strategies

Informed by the taxonomy of behaviour change techniques used in interventions and the behaviour change wheel²², a range of evidence-based behavioural techniques will be employed to motivate and support lifestyle change. This will include motivational interviewing, increasing self-efficacy, formation of specific implementation intentions, self-monitoring, personalised action and coping plans, feedback, re-enforcement and social support. To facilitate behaviour change, participants will be offered access to an equipment tool kit (e.g. pedometers, resistance bands and DVDs). Emphasis will be placed on self-monitoring and goal setting, physical activity through pedometers, with weekly feedback in the first week of each phase. In phase 3, the importance of regular self-weighing will be stresses and feedback provided at each telephone consultation.

Programme delivery

The programme design I based on a combination of:

• What might be practically delivered in the NHS by CRC clinical nurse specialists (with relevant training) estimated at a total of 6-8 hours input with each patient over a 31 week period.

- Current evidence on personalisation and frequency of contact in behavioural change literature (indicating the value of one to one contacts).
- The average age of participants (more familiar with one to one contact rather than electronic counselling).
- The need for different emphasis about lifestyle changes in each treatment phase.

For the purpose of this feasibility study, the intervention will be delivered by two part time dedicated TreatWELL LCs who will work closely with the CRC clinical nurse specialists. The LCs will have a nursing background with bespoke TreatWELL training. A protocol for referral procedures to specialist NHS staff (e.g. dietician, physiotherapist) will be in operation. Each participant will be seen for a minimum of 3 face to face visits (one per intervention phase) plus 6 to 12 support telephone consultations (depending on duration of adjuvant therapy, during which time they will continue to receive telephone support). The main communication format will be verbal (considering poor literacy and numeracy skills and visual difficulties that may be present tin this age group). However, all advice will be supported by written materials (and DVD in the case of exercise) to re-enforce guidance and share with family / NHS staff. The intervention sessions will be delivered in Ninewells Hospital, Dundee.

Usual care procedures

Participants will continue to receive usual care procedures (including nutritional screening using the MUST tool and ERAS procedures. In phase 3 all participants will be provided with information on self-management of lifestyle change, e.g. through the ALISS programme (www.aliss.scot.nhs.uk/), to help connect participants with community based and third sector activities (e.g. Move More Dundee).

Exit strategy

Participants with a BMI<20 or >35kg/m² will be offered referral to the NHS dietetic service.

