2.1.1 Primary Research Questions

(i) What is the uptake of the proposed intervention programme during the period between diagnosis and surgery?

- What are the recruitment levels that can be achieved within the study duration and how do these vary between disease status and socio-demographic factors?
- How soon after diagnosis can patients commence the intervention programme?

(ii) Can all of the intervention components be delivered in the intervention phases?

- Can the programme be successfully implemented within the NHS setting?
- What is the actual length of time in each phase?
- What is the intervention fidelity to the TreatWELL protocol, which areas present delivery challenges and why?

(iii) What are the responses of patients to the intervention programme and evaluation measures?

- To what extent are patients able to achieve smoking, physical activity and dietary change before, during and after treatment (adherence)?
- Can the proposed evaluation measurements on behavioural and health outcomes (relevant for future RCT) be undertaken successfully?
- What is the retention rate at the end of the study period?

(iv) What are the patients' views on the intervention programme?

- How acceptable are the intervention recruitment methods, programme content, delivery, intensity and exit strategy to participants?
- What factors do patients think influence adherence?

(v) What are the intervention programme delivery costs?

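### Section 3.1 sets the planned telephone calls both as at least 12 and as 6 to 12, so completeness of delivery has no single reference

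*Protocol*

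**What the plan says.** Section 3.1 (Study description) gives the contact schedule twice.

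- The opening paragraph says that the lifestyle counsellors deliver the programme by "three face to face contacts and a minimum of 12 phone calls". No subgroup or condition is attached to the number of calls.
- Under Programme delivery, the visits are stated as "Each participant will be seen for a minimum of 3 face to face visits (one per intervention phase", and the calls as "plus 6 to 12 support telephone consultations (depending on duration of adjuvant therapy", with telephone support continuing during that therapy.

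Three other statements in section 3.1 bear on the contact load. On phase 1 calls: "Two telephone calls will be made to participants in the pre-surgery period". On the phase 1 visit: "In phase 1, participants will be seen for a one hour session". On total counsellor time: "estimated at a total of 6-8 hours input with each patient over a 31 week period".

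Delivery is one of the primary research questions. Section 2.1.1, question (ii), asks: "Can all of the intervention components be delivered in the intervention phases". Sections 2.2.3 and 8 say that the counsellors' pro-formas, one completed after every contact, will be analysed for completeness of delivery.

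**The concern.** Both statements are in current text and describe the same quantity for the same participants, yet one uses 12 as a lower limit and the other as an upper limit. Completeness can only be judged against a planned amount, and here the protocol offers two. With no reference named, the standard could be settled after the delivery records have been seen.

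There is also a practical consequence before any analysis. The programme is delivered by two part-time counsellors. One could aim for at least 12 calls for everyone, and the other for as few as 6 where adjuvant therapy is short or absent, and both would be following the document. Since the study is meant to inform a randomised trial, an unclear contact schedule would carry over into that trial's definition of the intervention and its staffing.

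**Working it through.** The protocol gives no derivation of the number of calls, so there is no figure to reproduce. The related arithmetic is sound: the phases are given as "3 weeks in phase 1, 3 weeks in phase 2, 25 weeks in phase 3; total intervention period 31 weeks", and 3 + 3 + 25 = 31; the expected sample of 34 out of 48 eligible patients is 34/48 = 70.8%, stated as 71%.

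**Inputs.** Calls per participant, n: n ≥ 12 (section 3.1, opening paragraph) and 6 ≤ n ≤ 12 (section 3.1, Programme delivery). Expected participants: 34 (sections 4.1 and 8.1); the protocol summary gives 30.

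**Step 1: where the two statements agree.** The sets {n ≥ 12} and {6 ≤ n ≤ 12} share one value, n = 12. Counts of 6, 7, 8, 9, 10 and 11 satisfy only the second statement. Counts above 12 satisfy only the first.

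**Step 2: size of the shortfall for one participant.** Calls delivered divided by the first statement's minimum of 12:

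| Calls delivered | Share of 12 |
|---|---|
| 6 | 50% |
| 7 | 58% |
| 8 | 67% |
| 9 | 75% |
| 10 | 83% |
| 11 | 92% |
| 12 | 100% |

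Every row lies within the second statement's range.

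**Step 3: size over the study.** Minimum planned calls for 34 participants: 34 × 12 = 408 against 34 × 6 = 204, a difference of 204. For 30 participants: 360 against 180, a difference of 180. These differences are upper bounds, because they put every participant at the bottom of the 6 to 12 range. If everyone were planned for 12, the difference would be zero. The protocol does not give the proportion expected to have adjuvant therapy, so no value in between can be fixed.

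**Step 4: can the rest of the protocol decide between them?**

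- The adjuvant-therapy condition explains variation between 6 and 12. It does not explain a floor of 12 for everyone.
- In the Programme delivery sentence the minimum attaches to the visits. Even if it is stretched to cover the calls, the floor becomes 6, not 12.
- The two phase 1 calls fit either total.
- The time budget fits either total. Assume that each of three visits lasts one hour (stated only for phase 1). Then 6 to 8 hours leave 3 to 5 hours, or 180 to 300 minutes, for calls. Twelve calls would take 180/12 = 15 to 300/12 = 25 minutes each; six calls would take 180/6 = 30 to 300/6 = 50 minutes each. Neither is excluded.

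**The case against.** The strongest reply is that the harm is limited. A pro-forma is completed after every contact and records contact time, so the actual number of contacts can be reported whichever plan is taken as the reference. The study has one arm, tests no hypothesis and treats its outcome results as indicative. All of this stands, and it lowers the severity. It does not remove the conflict: a count of contacts shows what was done, but completeness needs to know what was planned. Nor can this be left to an analysis plan, which cannot decide how many calls the counsellors should make.

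Several stronger readings are tempting, and the protocol does not support them.

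- **Visits.** A reader might infer that the face-to-face contacts are contradictory too, since they are three in one place and at least three in the other. Three visits, one per phase, satisfy both, so this is loose wording.
- **Fidelity.** A reader might infer that the fidelity measure has two standards. Section 2.2.3 records fidelity as the counsellor's perceived rating of content and approach, and no number of calls enters it.
- **Cost.** A reader might infer that the cost result for research question (v) is undefined. Section 2.2.5 takes cost from time sheets and consumables, that is, from what was delivered. The conflict reaches cost only through the schedule the counsellors choose to follow.
- **Pass or fail.** A reader might infer that participants will be classed as delivered or failed. The protocol sets no such score or threshold. The percentages above show the distance between the two statements; they are not results of a planned metric.
- **Participants without adjuvant therapy.** A reader might infer that they are planned for fewer than 12 calls. The protocol links the number to the duration of therapy but assigns no number to any group.

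**Conclusion.** The point holds for the telephone calls. Section 3.1 gives two planned numbers that agree only at 12, and nothing else in the protocol settles which one applies. Participants with 6 to 11 calls meet one statement and miss the other, by up to half of the larger minimum. Over the expected 34 participants the difference in minimum planned calls is at most 204; that figure assumes every participant is planned at 6 under the second statement.

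The direct consequence is confined to completeness of delivery under research question (ii) and to consistent delivery by the counsellors. Sample size and participant safety are not affected. This is an inconsistency that should be fixed.

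**What to change.** Before recruitment, the study team should reconcile the two statements in section 3.1 into one planned contact schedule and use it in both places. If the number is meant to depend on adjuvant therapy, the schedule should state it by adjuvant-therapy status. The number of visits can be worded the same way in both places at the same time. Completeness of delivery should then be reported against that schedule, together with the actual number of contacts per participant. Which number of calls is right is for the study team to decide.

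The cost is protocol wording only, with the approvals that section 11.1 requires for any amendment. No data collection changes, because the pro-formas are already completed after every contact.

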3.2 STUDY FLOWCHART

3.3 STUDY MATRIX

| Time | T0 Baseline | T1 End of phase 1 | T2 End of phase 2 | T3 End of phase 3 |
|---|-------------|----------------------|----------------------|----------------------|
| Collection of socio-demographic, | Х | | | |
| background and clinical information | | | | |
| Medication usage | Х | Х | Х | Х |
| Self-reported smoking | Х | Х | Х | Х |
| Self-reported alcohol intake | | | | |
| Scottish physical activity | Х | Х | Х | Х |
| questionnaire | | | | |
| Six minute walk test | Х | Х | Х | Х |
| DINE (dietary) questionnaire | Х | Х | Х | Х |
| Physiological measures (weight, | Х | Х | Х | Х |
| height, waist circumference, skin fold) | | | | |
| Fatigue (MFI-20) | Х | Х | Х | Х |
| Bowel function (LARS) | Х | Х | Х | Х |
| Quality of life (EORTC C29 & C30) | X | Х | Х | Х |
| Adverse event recording | | Х | Х | Х |
| Acceptability interview (1 in 3, n=10) | | | Х | Х |

4 STUDY POPULATION

Patients diagnosed with CRC and beginning treatment at Ninewells Hospital, Dundee.

4.1 NUMBER OF PARTICIPANTS

Over a 5 month recruitment period, it is estimated that 60 patients will be diagnosed with CRC and begin treatment. Based on our previous lifestyle trial in CRC patients¹³ it is estimated that 48 of 60 patients will meet the inclusion criteria and 34 (71%) will agree to participate.

4.2 INCLUSION CRITERIA

Adults (i.e. aged 18 years and over), who are capable of giving informed consent, with stage I to III colorectal cancer, who are eligible for potentially curative treatment (must be fit for major surgery) will be included in the study

4.3 EXCLUSION CRITERIA

Patients who:

- have been diagnosed with severe cognitive impairment,
- have emergency surgery,
- are receiving pre-operative neo-adjuvant therapy.

5 PARTICIPANT SELECTION AND ENROLMENT

5.1 IDENTIFYING PARTICIPANTS

When patients receive their cancer diagnosis they are routinely referred to the clinical nurse specialist (CNS) to discuss treatment and care plans. At present, the CNS provides brief (2-3 minutes) lifestyle advice. During the study, the CNS will inform eligible patients about the study and endorse the importance of the study for helping achieve lifestyle change in the pre

surgery period. Pateints will be asked if they would be interested in taking part, or in hearing more about the study, and those interested will be introduced to the TreatWELL research nurse (RNS) (up to 10 days of diagnosis) who will be present at the clinic.

If patients indicate to the CNS that they are happy to be introduced to the research nurse, the RNS will provide face to face verbal and written information about the study and request permission to re-contact patients within 48 hours, allowing at least 24 hours to consider taking part in the study. Patients details will be collected by the RNS on a response form. Information will include a participant information sheet and an invitation and endorsement letter from the lead CRC clinician for Tayside..

5.2 CONSENTING PARTICIPANTS

On re-contact, participants who wish to participate will be given a unique identifier and will be invited to complete informed consent and an appointment will be made for baseline measures (at Ninewells Hospital). Informed consent will be taken by the research nurse, one copy will be filed securely in the trial master file and one copy will be given to the participant. As part of the informed consent process the patient will be asked for their permission to inform their GP that they are taking part in the study, once given, the participant's GP will be informed that they are taking part and will be given a copy of the participant information sheet.

5.3 SCREENING FOR ELIGIBILITY

The CNS will screen all participants diagnosed with CRC over a 5 month recruitment period for eligibility.

5.4 INELIGIBLE AND NON-RECRUITED PARTICIPANTS

During the informed consent process, individuals will be informed that they can decline to consent to take part and their care will not be affected. Information on reasons why patients choose not to participate and demographic characteristics will be recorded if patients wish to provide that information.

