2.2.1 Recruitment, retention, socio-demographic and clinical data (RQ i, iii)

The research nurse will prospectively collect details on socio-demographic background, clinical information (including tumour stage and site), type of surgery, stoma status, medications and details of adjuvant treatments. Post-surgical morbidity and hospital stay will

also be recorded. Adverse events (including GP visits and hospital admissions) will be reported at each assessment.

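### Variation in uptake by disease status and socio-demographic factors is part of a primary question, but the protocol secures those variables only for patients who agree to take part

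*Protocol*

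**What the plan says.** Section 2.1.1 lists under primary question (i): "What are the recruitment levels that can be achieved within the study duration and how do these vary between disease status and socio-demographic factors".

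The matching data provision is section 2.2.1, which is mapped to questions (i) and (iii): "The research nurse will prospectively collect details on socio-demographic background, clinical information (including tumour stage and site), type of surgery, stoma status, medications". The study matrix in section 3.3 marks the row beginning "Collection of socio-demographic", which also covers background and clinical information, at T0 only. Section 5.2 places the baseline appointment after the decision to join: "participants who wish to participate will be given a unique identifier and will be invited to complete informed consent".

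For patients who do not join, section 5.4 provides: "Information on reasons why patients choose not to participate and demographic characteristics will be recorded if patients wish to provide that information".

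Screening is wider than consent. Section 5.3 states: "The CNS will screen all participants diagnosed with CRC over a 5 month recruitment period for eligibility". Eligibility under section 4.2 covers adults "with stage I to III colorectal cancer, who are eligible for potentially curative treatment", so stage has to be established at screening. No section says which variables are kept for patients who are screened and then decline. Section 5.1 mentions a response form completed by the research nurse. Its content is not specified, and only patients who accept an introduction to the research nurse reach it.

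**The concern.** To say how recruitment varies by stage, site, age, sex or deprivation, one needs the factor for every eligible patient, whether or not that patient joined. The plan secures it for those who join. For decliners it offers a voluntary demographic item and no disease item.

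The study exists to inform whether and how to run a randomised trial (section 2). Which eligible patients take up the programme and which do not bears on that trial's recruitment plan and on the reach of its results. A statistical analysis plan cannot repair this, because it cannot recover variables that were not recorded. The recruitment window is five months, and the loss may be hard to make good afterwards.

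**Working it through.** **Inputs.** From sections 4.1 and 8.1: 60 patients diagnosed and starting treatment, 48 eligible, 34 (71%) agreeing.

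**1. Reproduce the plan's figures.** 48/60 = 80.0%. 34/48 = 70.8%, which rounds to the stated 71%. The exact 95% confidence interval for 34/48 is 56% to 83%. Overall uptake needs only the count of decliners, not their characteristics, so it stands.

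**2. Size of the gap.** Eligible decliners: 48 − 34 = 14, and 14/48 = 29% of the denominator. By the text, none of the 14 has a recorded disease variable. The number with demographics depends on willingness. If 30% to 70% volunteer (an assumption), that is 0.30 × 14 = 4.2 to 0.70 × 14 = 9.8, so about 4 to 10 patients.

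**3. What the data could then say.** Assume a binary factor with participants split 17/17, and k volunteering decliners split as evenly as possible into a and b. The other m = 14 − k decliners have an unknown level. Placing all m in one level or the other bounds the difference in uptake, A minus B:

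- lower bound = 17/(17 + a + m) − 17/(17 + b)
- upper bound = 17/(17 + a) − 17/(17 + b + m)

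| Decliners with the factor known | Difference in uptake compatible with the data |
|---|---|
| 14 of 14 | 0 (known exactly) |
| 10 of 14 (a = b = 5, m = 4) | −12 to +12 points |
| 7 of 14 (a = 3, b = 4, m = 7) | −18 to +24 points |
| 4 of 14 (a = b = 2, m = 10) | −31 to +31 points |
| 0 of 14 (disease status as written) | −45 to +45 points |

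In the last row the extreme is 17/17 = 100% against 17/31 = 55%.

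**4. Selection bias in the demographic comparison.** Suppose true uptake is equal, with 7 decliners in each level: 17/24 = 71% in both. If 6 volunteer in one level and 3 in the other, an analysis of known cases gives 17/23 = 74% against 17/20 = 85%, a false gap of 11 points. If 7 and 2 volunteer, it gives 17/24 = 71% against 17/19 = 89%, a false gap of 19 points. If all 14 volunteer, the bias vanishes.

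**5. Precision with complete data.** Assume all 48 are recorded, split 24/24, with 71% uptake in each level. The 95% half-width for the difference is 1.96 × √(2 × 0.71 × 0.29/24) = 1.96 × 0.131 ≈ 26 points.

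**The case against.** The strongest reply has five parts.

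- **Silence is not a rule against recording.** No section says that decliners' disease status goes unrecorded. The CNS sees stage when screening, section 2.2.1 does not say that it applies to consented patients only, and the response form might hold more. This stands as a limit on certainty: non-capture is inferred. But the matrix puts clinical data at T0, the response form misses anyone who refuses at the CNS step, and section 5.4, where non-participants are dealt with, lists reasons and demographics only.
- **Recruitment levels could mean numbers recruited per category.** Participant data would then suffice. Such counts, however, describe the sample and do not show how recruitment varies unless the eligible numbers per category are known.
- **The affected part is small.** It is one clause under one of five primary questions. No target or progression rule depends on it, and section 8.1 disclaims hypothesis testing. This stands and lowers the severity.
- **A complete record buys little precision.** This also stands: about ±26 points in the illustration. The gain is a description free of unknown selection, not a firm estimate.
- **Voluntary recording respects confidentiality.** Sections 10.1.1 and 10.1.2 restrict the release of clinical information and commit to data protection law. A row-level file crossing several variables for a few dozen patients at one hospital could be identifying. This stands and shapes the remedy.

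A reader might also infer that the demographic comparison is bound to be biased, or that patients least willing to join are least willing to give data. The documents support neither. Nor do the 12 ineligible patients (60 − 48) add to the problem, since they lie outside the uptake denominator.

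**Conclusion.** The concern holds in a limited form. Section 2.1.1 asks for variation in recruitment by disease status and socio-demographic factors. The data provisions supply those factors only for patients who agree. As written, uptake by disease status lacks a denominator for an expected 14 of 48 eligible patients (29%), and uptake by demographic factors is exposed to selection bias of unknown direction and size. The stronger conclusion, that recruitment cannot be assessed, is not supported: overall uptake and the other primary questions are untouched.

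The count of 14 rests on the protocol's own forecasts. The bounds and false gaps in the working rest on an assumed binary factor, an even split of participants and assumed volunteering, so they illustrate and do not predict. The reading that decliners' disease status is not kept rests on the absence of any provision for it. Severity: should be fixed, not must be fixed.

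**What to change.** Amend sections 5.3 and 5.4 so that the CNS keeps a minimal, non-identifiable screening record for each eligible patient: age band, sex, deprivation category, tumour site, stage, approached or not, and agreed or declined. Release it to the study team only as aggregate counts per factor (agreed and declined within each level), not as rows. State how this fits the commitments in sections 10.1.1 and 10.1.2, and make it subject to ethics approval. Keep reasons for declining voluntary, as now. Report uptake overall and by factor descriptively, with confidence intervals and without tests.

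The cost is a few minutes of CNS time per patient, who is being screened anyway, and a short protocol and ethics amendment. Counts per factor do not allow factors to be cross-classified, but question (i) does not ask for that. Subgroup estimates will remain imprecise at this size, and the report should say so.
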